- 22. Patients with bleeding disorders that would, in the opinion of the Investigator, interfere with the performance of study procedures; patients taking coumarins (e.g. Warfarin) or other anticoagulants (e.g. enoxaparin or direct thrombin inhibitors).
- 23. Any circumstance in which the investigator deems participation in the study is not in the subject's best interest.
- 24. Use of any investigational product within 3 months of the injection without receiving prior written consent of the Medical Monitor.

Number of Sites: Up to 10 clinical centers will be included in the study.

Study Duration: 18 months NKA injections follow up followed by 24 month long term follow up for a total study duration of 42 months.

Study Enrollment: Up to 30 subjects undergoing NKA injection will be enrolled into the study. Patients who have received a single injection of NKA under previous research protocols may enroll in this clinical trial to receive a single additional injection. Patients who have never received an NKA injection may enroll in this clinical trial for up to a total of two (2) NKA injections, temporally spaced at least 6 months apart. All biopsies are to be taken from a single kidney, and all NKA injections are to be given into the kidney that was biopsied. Patients who complete screening procedures satisfying all I/E criteria will be enrolled into the study immediately prior to the injection. Patients who do not meet all criteria before injection will be considered screen failures. Once a patient has been injected, the patient will have completed treatment and every effort should be made to ensure the patient completes all follow-up visits. Injection dates for the first 3 patients receiving their second NKA injection will be staggered by a minimum of 3 week intervals to allow for assessment of acute adverse events and other safety parameters by the DSMB. Subsequent second injections will continue to be staggered so as to occur no less than 3 weeks apart, but individual DMSB review will not be required. At the completion of the follow-up visits, patients will continue in a long-term follow-up study. Patients will be followed for a total of 36 months following the last NKA injection under this protocol, whether the first or second injection.

Investigational Plan:

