It is anticipated that all patients will be planned to receive 2 injections under this protocol, in order to allow dose-finding and to understand the duration of effect. Under certain circumstances a patient or investigator may decide to postpone or withhold the second dose. In general, if there appears to be any untoward safety risk, in situations including rapid deterioration of renal function, the development of uncontrolled diabetes, or the development of uncontrolled hypertension, or if there is the intercurrent development of a malignancy, the patient should not receive the second dose.

Second injections under this protocol will be staggered so that single injections in different patients occur no less than 3 weeks apart. The DSMB will review the clinical data regarding each of the first 3 second injections under this protocol, and will consult with the Sponsor before the 2nd, 3rd, and 4th second injections are made. Subsequent second injections will continue to be staggered so as to occur no less than 3 weeks apart, but individual DMSB review will not be required.

No staggering will be required for first NKA injections under this protocol.

Post-Injection Follow-up: Subjects will return to the clinic for follow-up safety assessments on Days 7, 14, and 28 post-injection and at 2, 3, and 6 months post-injection. At 6 months post-injection, post-treatment MRI and renal scintigraphy studies will be conducted. After patients complete the 6 month efficacy visit, they will be considered for a second NKA injection. Patients receiving a second dose will follow the same follow up visits that occurred after first injection. Patients 6 month post first injection visit will serve as the patients 14 to 10 day pre- second injection visit. Patients will return for their second injection and at 2, 3, and 6 months post-injection Patients will be followed up to 18 months in the post follow up phase with 6 months after first NKA injection and 12 months after second NKA injection. Refer to the time and events schedule on page 14 for additional post follow up time points.

Long Term Follow-up: Patients will be followed for safety and efficacy for 24 months after the 18 month initial follow up period. Telephone contact will be made 24 and 36 months after the last NKA injection, and visits will be made at 30 and 42 months after the last NKA injection.

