10.3 Subject Withdrawal and Replacement

Subjects may withdraw from the study at any time and for any reason. If the PI determines that continuing in the study is no longer in the best interest of the subject, then the PI should withdraw the subject from the study. If a subject withdraws from the study, the reason for withdrawal should be documented.

If a subject withdraws from the study before having a biopsy, the subject will be considered a screen failure. If a subject withdraws from the study after having the biopsy, but before injection of NKA, the subject will not be a screen failure, but will not be considered enrolled, and may be replaced. If a subject withdraws from the study after injection but before the end of the follow-up period, the subject cannot be replaced. A maximum of 30 subjects, including subjects previously injected in the two previous Phase 1 trials, will be injected with NKA. Every effort should be made to ensure that patients who have been injected with NKA return for all subsequent follow-up visits and procedures.

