13.5 Data Safety Monitoring Board

Given the uniqueness of this product, an external data safety monitoring board (DSMB) will be convened to oversee patient safety, especially as it relates to any unexpected product-related events. The committee will be composed of a minimum of 3 members whose expertise is such that the Board has adequate familiarity with reconstructive urological surgery, renal medicine, and monitoring emerging safety issues in clinical studies. The DSMB will be an independent committee that is not otherwise engaged in the conduct of the clinical study and who do not have conflicts of interest.

The DSMB will be governed by the DSMB charter. The specific mandate of the DSMB will be to review any AE's/SAE's assessed by the PI as related to the investigational product, NKA. Thus, any events assessed as related to NKA will be forwarded to the DSMB by the study site or CRO. If the event is rated mild or moderate, the DSMB will work with the PI and Medical Monitor to determine the best course of action. The "best course of action" may range from no changes to adaptations of procedures to prevent future events, etc. If the event is severe or life-threatening, then the DSMB may consider halting future injections until a best course of action is devised. If the event is an SAE that is considered severe or life-threatening, then no future patients may be injected until approved by the DSMB. In addition to the above, the DSMB will

be charged with reviewing the safety data from the first two patients injected and providing consultation on enrollment of subsequent patients.

The DSMB will be expected to advise RegenMed (Cayman) Ltd. regarding the study design and study conduct, and may recommend early study termination for safety reasons. The DSMB will be expected to request additional information and analyses as they require. The DSMB's recommendations will be communicated to the study centers, and where required to the IRBs/ECs and the Competent Authorities. If the DSMB recommends stopping the study, the Competent Authorities and the IRBs/ECs will be notified.

The surgical procedures used in this study, renal biopsy, percutaneous needle insertion in the kidney, and laparoscopic or retroperitoneoscopic surgery, are established procedures with known adverse event profiles. However, if unexpected procedure-related events occur, the DSMB will review the events on a case-by-case basis.

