13.6 Stopping Criteria

Approximately two to three weeks following each of the first two injections, the PI, Medical Monitor, DSMB and RegenMed (Cayman) Ltd. staff will review the case to assess both positive and negative results of the injection. If no clinically significant unexpected events are identified, the next patient may be injected such that the timing between the first 3 injections will be staggered by 3 weeks. If any of the following events occur, no additional patients can be injected until review by the DSMB is completed:

- 1. An SAE that is rated as severe or life-threatening and considered related to NKA or study procedures by the PI
- 2. Death of an enrolled patient
- 3. Similar SAE's in more than one patient that are considered related to NKA by the investigator
- 4. Inability to deliver a minimum of 50% of the dose of NKA in more than one patientdue to surgical or other issues
- 5. DSMB recommendation to temporarily stop enrollment to allow for more precise review of case(s)

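### The mandatory safety pauses in 13.5 and 13.6 are worded by patient, so read literally they do not hold a second injection in a patient already injected under this protocol

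*Combined protocol and SAP*

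**What the plan says.** Section 13.6 lists five triggers: a severe or life-threatening related SAE, a death, similar NKA-related SAEs in more than one patient, failure to deliver half the dose in more than one patient, and a DSMB recommendation to stop enrollment temporarily. The consequence is: "If any of the following events occur, no additional patients can be injected until review by the DSMB is completed".

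Section 13.5 has a second mandatory pause. For a severe or life-threatening SAE related to NKA, "then no future patients may be injected until approved by the DSMB". The sentence before it, on severe or life-threatening related events generally, is worded by injection but is discretionary: "the DSMB may consider halting future injections until a best course of action is devised".

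On dosing, the synopsis (Injection) states: "It is anticipated that all patients will be planned to receive 2 injections under this protocol". For patients new to NKA, the synopsis (Study Enrollment) requires the two injections to be "temporally spaced at least 6 months apart". Phase 1 patients may receive one injection here. Section 10.3 sets the cap: "A maximum of 30 subjects, including subjects previously injected in the two previous Phase 1 trials, will be injected with NKA". Section 10.1 counts a patient as enrolled when injected.

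The synopsis also places controls on second injections. They must be at least 3 weeks apart, and the DSMB reviews the first three and "will consult with the Sponsor before the 2nd, 3rd, and 4th second injections are made". After that, no individual DSMB review is required. For first injections: "No staggering will be required for first NKA injections under this protocol".

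**The concern.** The pauses exist so that nobody is exposed to NKA while a serious signal is under review. A patient waiting for a second injection is still to be exposed, and in the same kidney as before, but has already been enrolled and injected. Taken at face value, that person is neither an additional patient nor a future one. The mandatory rule would then hold new entrants and leave re-injections to the DSMB's discretion or to the investigator's judgement about the individual.

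At stake is whether a second injection could be given after a death or a severe related SAE before the DSMB has finished its review. The question sharpens late in the trial, when second injections are the only ones left. A mandatory stop should not depend on how a site, the sponsor or the DSMB interprets it.

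**Working it through.** The documents give no figure on this point. The check is a comparison of the texts, then a bound on the number of injections exposed.

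**Step 1. What each provision covers, read literally.**

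| Provision | Worded by | Automatic? | Holds a second injection in a patient already injected here? |
|---|---|---|---|
| 13.6, five triggers | patient | yes | no |
| 13.5, severe or life-threatening related SAE | patient | yes | no |
| 13.5, severe or life-threatening related event | injection | no, DSMB may consider it | only if the DSMB decides so |
| 13.6, item 5 | enrollment | only as a trigger | not named; enrollment occurs at injection (10.1) |
| Synopsis, 3-week stagger | second injection | yes | sets spacing; not a stop |
| Synopsis, DSMB consultation | second injection | yes, by schedule | only around the 2nd to 4th; not triggered by events |
| Synopsis, advice to withhold the second dose | patient's own risk | no, stated as general advice | that patient only; not study-wide |

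No row is an automatic, event-triggered, study-wide hold on second injections. A Phase 1 patient not yet injected under this protocol can be read as an additional patient, so the gap concerns only patients already injected here.

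**Step 2. Second injections that could fall due during a pause.** The input from the synopsis is a minimum of 3 weeks between second injections in different patients. The pause length *w*, in weeks, is an assumption because the documents give none. A run of *n* injections at that spacing spans at least 3(*n* − 1) weeks, so at most floor(*w*/3) + 1 fit:

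- *w* = 2: floor(0.67) + 1 = 1
- *w* = 4: floor(1.33) + 1 = 2
- *w* = 8: floor(2.67) + 1 = 3
- *w* = 12: floor(4) + 1 = 5

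These are maxima. They assume second injections run at the fastest allowed pace throughout the pause and that the narrow reading is applied.

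**Step 3. After the last entry.** Once the last patient has had a first injection under this protocol, no additional or future patient remains, so the literal pause stops nothing. If that last patient is new to NKA and is re-injected, this phase lasts at least 6 months, the minimum interval between the two injections. How many second injections remain then depends on the accrual rate, which the documents do not give.

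**The case against.** The strongest reply is that the narrow reading is not the natural one. The sentence just before the rule in 13.6 lets the next patient be injected with the first three injections staggered by 3 weeks. In the synopsis that stagger belongs to second injections, which are counted by patient, and first injections need none. Read together, the next patient, and so an additional patient, can include one due a second injection. This stands as a plausible reading, but the text does not settle it. Section 13.5 has the DSMB review the first two patients injected and advise on enrolling later ones, and item 5 of 13.6 speaks of enrollment; both point towards entry. Section 13.5 also uses the word injections where it means injections, one sentence before its patient-worded pause.

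The second reply is practical. Sites hold no stock: product is made and shipped only after the site confirms eligibility at the pre-injection visit (8.2.2, 9, 11.3). SAEs reach the sponsor within 24 hours (13.3.4). NKA-related events go to the DSMB, which may halt injections or recommend termination (13.5). A reader might infer that one site could readily inject while another holds. The documents do not support that as a likely event, because the sponsor's side has a gate before each dose; the clearest exception is product already shipped when the trigger occurs. These controls reduce the risk, but none is a written rule that second injections stop.

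Third, the DSMB charter governs the DSMB's specific activities and is not among the documents. It may be clearer. Even so, sites work from the protocol.

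**Conclusion.** The point holds as a gap in wording. Read literally, the two mandatory pauses do not hold second injections in patients already injected under this protocol, and nothing else in the documents does so automatically. Exposure is at most about 1 to 5 second injections per pause, for assumed pauses of 2 to 12 weeks at 3-week spacing, and only if a trigger occurs and the narrow reading is applied.

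Two stronger readings should be set aside. A reader might infer that about half the planned injections are unprotected: 30 of 2 × 30 = 60 (50%) with 30 new patients, or 23 of 2 × 23 + 7 = 53 (43%) if all 7 Phase 1 patients return. Those are all the second injections in patients already injected here; only those falling due during a pause are exposed. A reader might also infer that the plan intends re-injection to continue during a safety review. The documents do not say so, and the stagger sentence in 13.6 gives some support to the opposite.

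Severity is minor to moderate: a wording fix, but to a safety rule.

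**What to change.** In 13.5 and 13.6, replace the patient-worded pause with: *no further NKA injections, first or second, in any patient, until DSMB review is completed*. Section 13.5 makes release depend on DSMB approval rather than completed review; if the sponsor wants that condition, keep its ending and change only what is held. In item 5 of 13.6, write *stop enrollment or injections*. Items 1 to 4 can stay. Check that the DSMB charter matches.

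The change is a few words in an amendment and needs no extra patients. It has an operational cost. The month 6 visit doubles as the pre-injection visit and must fall 10 to 14 days before the second injection (11.4), so a held injection may miss that window. Some eligibility checks may then need repeating; 11.3 exempts scintigraphy when an injection is delayed. Held injections must afterwards queue at 3-week spacing, so a pause may delay several patients. The amendment should say which checks are repeated after a hold.

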10 STUDY POPULATION

10.1 Eligibility Criteria

Eligibility criteria should be assessed at Screening. In addition, unless otherwise noted for the specific criterion, eligibility criteria should be also be reviewed before the biopsy and at the Day -10 to -14 pre-injection visit.

Up to 30 subjects will be enrolled in this study, including subjects previously injected in either Phase 1 trial. Note that a subject will be considered enrolled into the study at the time of injection.

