13.3.2 Recording of Serious Adverse Events

All SAE's should be recorded in the AE CRF from first study procedure through the 6 month follow-up visit. In addition, any SAE's that occur during the long-term observational phase AND are considered related to investigational product, should be recorded in the CRF. All SAE's should be reported according to the procedures discussed below (Section 13.3.4). **13.3.3 Follow-Up of AE's/SAE's**

All AE's that are assessed as related to Investigational Product (i.e., NKA) or study procedures (e.g. biopsy, laparoscopic surgery, or surgical or percutaneous injection) should be followed by the Investigator until the event resolves, stabilizes, or returns to baseline. The investigator should continue to report any significant follow-up information to the Sponsor or Sponsor's designee up to the point the event has been resolved.

SAE's should be followed until the event resolves, stabilizes, or returns to baseline. If the patient insists on discontinuing from the study prior to resolution/stabilization/return to baseline of the SAE, then the patient will continue to be followed as part of the SAE reporting system. That is, the Investigator will continue to follow the patient on a schedule dictated by the clinical situation and submit appropriate follow-up SAE reports as discussed in Section 13.3.4. If the patient refuses to continue to follow-up with the Investigator, then the Investigator may follow the patient through consultation with the patient's primary physician if allowed by the site-approved ICF and applicable regulations.

SAE's that are identified on the last scheduled visit must be recorded in the AE CRF and reported to the Sponsor or Sponsor's designee as outlined in Section 13.3.4. Subjects with unresolved, previously reported serious adverse events, or new serious adverse events identified on the last scheduled visit, should be followed by the investigator until the events are resolved, stabilized, or returned to baseline.

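### The stopping rule in 13.6 holds injections but not study biopsies, and its death trigger does not reach patients between biopsy and first injection

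*Combined protocol and SAP*

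**What the plan says.** Once any of the five triggers in 13.6 occurs, "no additional patients can be injected until review by the DSMB is completed". The triggers that matter here are:

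- Trigger 1: "An SAE that is rated as severe or life-threatening and considered related to NKA or study procedures by the PI".
- Trigger 2: "Death of an enrolled patient".
- Trigger 5: a "DSMB recommendation to temporarily stop enrollment".

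Section 10.1 fixes the meaning of enrolment: "a subject will be considered enrolled into the study at the time of injection". The synopsis (Study Enrollment) places it immediately before injection. Section 10.3 says of someone who withdraws after biopsy but before injection that "the subject will not be a screen failure, but will not be considered enrolled, and may be replaced". Section 11.2 puts the biopsy 4 to 14 weeks ahead of the injection, and 13.3.3 gives biopsy as an example of a study procedure.

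Section 13.5 contains a second hold, for severe or life-threatening SAEs related to NKA. It too is limited to injections. For procedures, 13.5 says that "if unexpected procedure-related events occur, the DSMB will review the events on a case-by-case basis".

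**The concern.** Two things look out of line.

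First, the action does not match the cause. If a biopsy produces a severe bleed, the rule suspends a different procedure and says nothing about the next biopsy. Up to 10 sites may be taking biopsies, and no section staggers them. Section 9 and 12.5.1 keep the affected patient from being injected, but they do not protect the next patient.

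Second, an all-cause death trigger is useful because it does not depend on the investigator's causality call. That protection starts only at injection. Before then, a death holds the trial automatically only if the investigator attributes it to a study procedure. The relationship scale in 13.2.1 gives little help: it is meant to cover study procedures, but its criteria are written mainly around NKA injection.

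At stake is whether patients are biopsied before an independent board has looked at a serious biopsy harm, and whether a death in the biopsy period automatically reaches that board.

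**Working it through.** The plan has no figure to reproduce; 14.1 says no formal sample size calculation was made. The main check is of wording.

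**Step 1. Run three events through triggers 1 to 4.** Trigger 5 is the DSMB's own decision and is left out.

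| Event | T1: severe related SAE | T2: death, enrolled | T3: similar NKA-related SAEs | T4: dose not delivered | Automatic action |
|---|---|---|---|---|---|
| Severe biopsy SAE, judged related | Met | No | No | No | Injections stop; biopsies not addressed |
| Death between biopsy and first injection, judged unrelated | No | No (not enrolled) | No | No | None |
| Same death after injection | No | Met | No | No | Injections stop |

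Section 10.3 speaks of withdrawal rather than death, but it agrees with 10.1 and the synopsis on status before injection. The gap concerns new patients, and returning Phase 1 patients who need another biopsy, before their first injection under this protocol. A patient awaiting a second injection is already enrolled and is covered.

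**Step 2. Number of biopsies.** At most 30 patients are injected (10.3), and 7 were treated in Phase 1 (section 6). If all 7 return and their frozen cells suffice, 30 − 7 = 23 biopsies are needed; otherwise up to 30, plus replacements.

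**Step 3. Biopsies done during a review.** This is biopsies per week × weeks of review, and neither is given. As an illustration only, assume 30 biopsies over 24 or 12 months and a review of 2 or 4 weeks: 30/104 × 2 = 0.6 to 30/52 × 4 = 2.3 biopsies.

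**Step 4. Chance that a severe biopsy SAE occurs.** Section 13.4.1 gives about 3% for macroscopic haematuria and painful haematoma, but no severe-SAE rate. Assuming 0.3% to 1%, with P = 1 − (1 − p)^n: 1 − 0.997^23 = 6.7%; 1 − 0.99^30 = 26%.

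**Step 5. Time outside trigger 2.** Low: 23 × 4 × 7/365.25 = 1.76 patient-years. High: 30 × 14 × 7/365.25 = 8.05 patient-years.

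**Step 6. Chance of at least one death in that time,** P = 1 − (1 − m)^(patient-years). The documents give no mortality for this population, so 2% and 5% a year are assumptions. Section 6.1.2 cites about 16% for Medicare CKD patients aged 66 and over. Read as annual, that is shown as an extreme, since this trial takes ages 30 to 70 and excludes a life expectancy under 2 years.

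| Annual mortality m | 1.76 patient-years | 8.05 patient-years |
|---|---|---|
| 2% | 3.5% | 15% |
| 5% | 9% | 34% |
| 16% | 26% | 75% |

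These are deaths from any cause. For deaths caused by biopsy, the <0.01% in 13.4.1 gives at most 1 − 0.9999^30 = 0.3%.

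**The case against.** The strongest reply is that the DSMB already closes most of the gap. Trigger 1 compels a review of any severe procedure-related SAE, expected or not. Section 13.5 lets the board advise on study design and conduct and recommend termination. Its charter is not in the file and may provide for a biopsy pause. This stands, and it limits the size. A reader might infer that after a severe first biopsy event all 22 to 29 remaining biopsies (23 − 1 to 30 − 1) would go unpaused. The documents do not support that, because the compelled review can end in a pause. What remains is the interval before the board advises.

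A second reply is that an unrelated death in someone not yet injected says little about NKA, and that 13.5 treats biopsy as an established procedure with a known risk profile. That is a fair argument against stopping all biopsies and injections after every such death. It is a weaker argument against sending the death to the board, because the label of unrelated is the judgement an all-cause trigger is meant to check.

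Third, the protocol also uses the word enrolled loosely. The synopsis (Therapeutic Product) and 6.5.3 apply it to patients at biopsy, and 10.2 implies enrolment some weeks before the product is given. Some sites may therefore apply trigger 2 from biopsy. The explicit definitions still govern, and the mixed usage is itself a reason to define the term in 13.6.

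Three further readings are tempting and should not be pressed:

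- **Fatal events escape trigger 1** because 13.2.2 grades death separately. Most readers would count a fatal event as at least severe.
- **Antiplatelet washout drives the risk** in this period. The washout is 7 days either side of each procedure, so it covers 14 of the 28 to 98 days, only 7 of them after the biopsy.
- **Biopsies taken during a hold are wasted.** Under 8.2.2 cells are frozen, can be thawed later and are kept for up to 5 years, so the purpose is lost only if the hold becomes permanent.

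**Conclusion.** The point holds as a matter of wording. After a severe or life-threatening biopsy-related SAE, 13.6 stops injections and leaves biopsies to the DSMB's later advice. A death between biopsy and first injection that is judged unrelated meets none of the automatic triggers, although the same death after injection would.

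The practical size is modest. The number of biopsies at risk during a review is unknown, and probably small unless review is slow or accrual is fast. The death probabilities rest on assumed mortality and mostly measure background deaths, not biopsy harm. Neither part of the finding depends on those rates. The main uncertainty is the unseen charter, which could already contain a biopsy pause. This is a cheap improvement to a safety rule; it does not show that the trial is unsafe as designed.

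**What to change.** Amend three places.

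- **13.6, action.** When trigger 1 is met by a biopsy-related event, neither biopsies nor injections proceed until the DSMB review is complete. For any other trigger, the DSMB states whether new biopsies also pause.
- **13.6, trigger 2.** Reword to *death of any patient from biopsy onward, whether or not injected* (or from injection, for a returning patient who needs no new biopsy). Keep the existing injection hold, and leave any biopsy pause after an unrelated death to the DSMB.
- **13.5.** Forward all deaths from biopsy onward, and all severe procedure-related SAEs, to the DSMB. Check that the charter agrees.

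No extra patients or data are needed: 13.3.4 already requires SAEs to reach the sponsor within 24 hours from consent onward. There is a downside. The probabilities in step 6 are also roughly the chance of at least one additional injection hold, usually for a death that proves unrelated. Some patients may pass the 45-day screening window during a biopsy pause; 11.1 already provides for case-by-case repeat assessment. Tissue already collected can wait frozen.
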